#### Abstract:

Malignant ascites appear when cancer cells metastasize to peritoneal cavity and interfere the circulation of lymph and blood. Patients with malignant ascites suffer from abdominal fullness, abdominal pain, poor intake, decreased nutrition, disability, and eventually inability to further anticancer treatment. Malignant ascites put a heavy burden on patient, their family, society and health care system.

Malignant ascites from cancers of stomach, pancreas and biliary tract are more refractory to intravenous chemotherapy or intraperitoneal chemotherapy than ascites from ovarian or chemo-naïve colorectal cancers because of the inherent nature of chemoresistance. Paracentesis is a treatment with immediate effect but the ascites regrow rapidly and repetitive paracentesis puts patients on the risk of intraabdominal infection. Intraperitoneal infusion of OK-432 can reduce malignant ascites but with intolerable adverse effects of fever, chills, pain, vomiting and septation of ascites which limit the further paracentesis.

Cumulating clinical experience suggests a tolerable safety profile of immune checkpoint inhibitors compared to chemotherapy for patients with malignancy. One theoretical advantage of intraperitoneal administration of immune checkpoint inhibitors is the existence of abundant inflammatory cells, immune cells and mesothelial cells dispersed in the malignant ascites. In addition, both pembrolizumab and nivolumab have been administrated intraperitoneally without obvious toxicities in murine tumor models

At China Medical University Hospital, one hundred gastric cancer patients, 50 pancreatic cancer patients and 50 biliary tract cancer patients are registered and treated each year. Among them, more than 20 patients suffer from malignant ascites which will ultimately be managed by repeated paracentesis with increasing frequency. Till now, there is no reported or ongoing clinical trial to investigate the efficacy of intraperitoneal checkpoint inhibitor on the malignant ascites. In this project, we propose to evaluate the efficacy of immune checkpoint inhibitor (pembrolizumab or nivolumab) on the malignant ascites of patients with advanced gastric, pancreatic and biliary tract cancers.

The major works in the 3-year-project are summarized as:

- 1. Screening patients, executing intraperitoneal administration of immune checkpoint inhibitor (pembrolizumab or nivolumab), and evaluating the clinical response.
- 2. Ascites cells and malignant cells in ascites are to be analyzed using flow cytometry, immunohistochemical staining, exon sequencing and total mutational burden determination.
- 3. Correlation study using clinical characteristic, ascites data and clinical response.

# **Background:**

Malignant ascites are often noted in patients with ovarian, colorectal, gastric, pancreatic and biliary tract malignancy. Among them, malignant ascites from cancers of stomach, pancreas and biliary tract are more refractory to chemotherapy because of the inherent nature of chemoresistance which remains a major challenge to physicians. The incidence of malignant ascites varies according to the condition of patients when they are evaluated (Maeda H, World J Gastroenterol 2015). A report from Norway identified 6.2% of 356 patients with gastric cancer had malignant ascites at their initial diagnosis (Lello E, Acta Oncol 2007). A large retrospective study from China found ascites in 2.6% of 5542 patients at the initial diagnosis of gastric cancer, and in 3.7% of patients thereafter (Fang N, Tumour Biol 2014). For patients with gastric cancer in T2-3 stage at diagnosis, the incidence of malignant ascites reached 15.0% of 293 patients (Yajima K, Am J Surg 2006). It is estimated that 3%-6% of patients with gastric cancer have malignant ascites at initial presentation, and 10%-15% of patients treated with operation develop peritoneal recurrence with half of them to have malignant ascites. Therefore, 8%-13.5% of patients with gastric cancer suffer from malignant ascites (Table 1; Maeda H, World J Gastroenterol 2015).

Ref.	No. of patients	Period	Country	Status of primary disease	Incidence
Development of periton	eal dissemination				
Nakajima et al 	7060	1960-1988	Japan	After gastrectomy	14.2%
Nashimoto et al 	13002	2002	Japan	After gastrectomy	9.9% (related to death)
Development of ascites			100 T 100	and the second s	
Lello et al 	356	1980-2004	Norway	At initial diagnosis	6.2%
Yajima et al 	293	1988-2002	Japan	GC with T2-3 at diagnosis	15.0%
Fang et al 	5542	2007-2012	China	At initial diagnosis	2.6%
				During the course of disease	3.7%1
Kitayama et al	83	2006-2008	Japan	Peritoneal recurrence	40.0%
Tahara et al 	56	1993-1999	Japan	Peritoneal recurrence	46.4%

Table 1. Incidence of peritoneal dissemination and ascites development due to gastric cancer

(Maeda H et al., World J Gastroenterol 2015;21:10936)

Patients with advanced pancreatic cancer are also prone to have malignant ascites. Once diagnosed, most pancreatic cancer patients with malignant ascites died within 2 months (Zervos EE, World J Surg Oncol 2006). Ascites is seen in 20% of pancreatic cancer patients (Adam RA, J Am Coll Surg 2004), with cancer cells identified in less than half of patients (Zervos EE, World J Surg Oncol 2006). Takahara et al., retrospectively reported 15% of patients (73/494) with advanced pancreatic cancer and malignant ascites, with better prognosis for patients with synchromous ascites compared with patients with metachronous ascites (Takahara N, Pancreas 2015). As same as pancreatic cancer, biliary tract cancer is also a cause of primary tumor for patients with malignant ascites (Fig. 1; Ayantunde AA, Ann Oncol 2007; Ayantunde AA, Clin Med Diag 2012).

[figure not shown]

Fig. 1. Primary cancer types causing malignant ascites (Ayantunde AA, Clin Med Diag 2012)

Malignant ascites is usually associated with disease in late stage. Patients with malignant ascites have more morbidity than patients without ascites. The distended abdomen will limit and reduce patients' daily activity. Furthermore, patients with large amount of malignant ascites suffer from back soreness and abdominal pain which render them to take more pain killer and frequent paracentesis. Overall, malignant ascites put a heavy burden on patient, their family, society and health care system.

Treatment for malignant ascites depends on multiple factors including the general condition of patients, the nature of their malignancies, the amount and growing rate of ascites, and the availability of certain compounds. There are several choices for treating malignant ascites: systemic chemotherapy or antitumor therapy, intraperitoneal chemotherapy, intraperitoneal targeting therapy, and paracentesis. The response of malignant ascites to intravenous chemotherapy depends on the inherent chemosensitivity of the primary tumor, therefore, malignant ascites in patients with gastric, pancreatic and biliary tract are more resistant to intravenous chemotherapy, especially for patients refractory to lines of previous chemotherapy. Paracentesis is a treatment with immediate effect but the ascites grow rapidly, besides, it puts patients on the risk of intraabdominal infection. Chemotherapy administrated intraperitoneally theoretically kills the tumor cells and penetrates the tumor nodules by diffusion. Most commonly used agents for intraperitoneal chemotherapy are taxane, mitomycin-C, mechlorethamine, thiotepa, cisplatin and 5-fluorouracil. Generally, a temporary control can be achieved with ascites control rate 33%-85% depending on the chemotherapy yields better ascites control in patients with ovarian cancer than patients with GI tract cancers.

Intraperitoneal immunotherapies using tumor necrosis factor (TNF), interferon or OK-432 (picibanil) have been utilized clinically since early 1980s. However, administration of TNF or

interferon intraperitoneally has been proposed to improve the function of killer cells in the peritoneal space but their activity in human is still controversial (Gebbia V, In Vivo 1991; Cavazzoni E, Int J Clin Oncol 2013). OK-432, a penicillin-heat-treated powder of Streptococcus pyogenes A3, is instilled into the peritoneal cavity to control malignant ascites through its effect to activate cytotoxic T cells (Torisu M, Surgery 1983; Katano M, Anticancer Res 1998). Intraperitoneal administration of OK-432 results in a reduction of ascites in 50%-70% of patients. The major challenge of intraperitoneal OK-432 is the adverse effects which sometimes are intolerable to patients. More than 90% of patients receiving intraperitoneal OK-432 administration suffered from abdominal cramping pain, fever, chills, bowel distention, nausea and vomiting.

Intraperitoneal administration of catumaxomab, a chimeric trifunctional antibody against EpCAM, CD-3 and Fc Rs, obtained a significant and persistent reduction of ascites in patients with ovarian cancer (Burges A, Clin Cancer Res 2007). Although a survival benefit was not demonstrated in a phase II/III trial, catumaxomab prolonged the puncture-free survival time (52 vs. 11 days in ovarian cancer; 37 vs. 14 in non-ovarian cancer) (Heiss MM, Int J Cancer 2010). However, patients receiving catumaxomab suffered from pyrexia, nausea and vomiting, and the preliminary data needs further confirmation.

Immune checkpoint inhibitors have demonstrated efficacy for several types of tumor in recent years (Fig. 2). The advantage of immune check-point inhibitors compared with conventional chemotherapy includes the avoidance of non-specific killing of cells, the absence of chemotherapy-induced adverse effects and the generalization of activity across several types of malignancies. Cumulating clinical experience suggests the more tolerable safety profiles of immune checkpoint inhibitors compared to chemotherapy. Recent data suggest the immune checkpoint inhibitors are effective against cancers of gastrointestinal tract. Nivolumab is superior to best supportive care for patients with gastric cancer who failed at least two lines of systemic anticancer therapies (Kang YK, Lancet 2017). The combination of nivolumab with chemotherapy showed promising efficacy in first-line therapy of patients with gastric cancer (ESMO 2017) from the preliminary data of a large phase III clinical trial. Based on the available data, nivolumab has been proved by Japan Ministry of Health, Labor and Welfare for the treatment of patients with unresectable advanced or recurrent gastric cancer which has progressed after chemotherapy in September 2017. As well, another PD-1 inhibitor, pembrolizumab, received American Food Drug Agent (FDA)'s approval for the treatment of patients with PD-L1-positive recurrent or advanced gastric or gastroesophageal junction adenocarcinoma who have received 2 or more lines of chemotherapy in September 2017.

[figure not shown]

Fig. 2. Monoclonal antibodies against negative checkpoints enhance the immune response and turn immune-balance. (Suzuki S et al., JJCO 2016;46:191)

Both pembrolizumab and nivolumab have been administrated intraperitoneally without obvious toxicities in murine tumor models (Fessas P, Semin Oncol 2017; EMA report: pembrolizumab 2015; EMA report: nivolumab 2015). Pembrolizumab at a dose of 10 mg/kg given intraperitoneally on days 6, 10, 13, 16 and 20 after implantation led to tumor growth inhibition of 92.5% at day 20 in murine. Similarly, nivolumab at a dose of 10 mg/kg given intraperitoneally on days 7, 10 and 13 after implantation inhibited tumor growth by 76% at day 20.

At our hospital (China Medical University Hospital), about one hundred gastric cancer patients, 50 pancreatic cancer patients and 50 biliary tract cancer patients are registered and treated each year (Chiu CF, Gastroenterol Res Pract 2016; Chiu CF, Springerplus 2016, Report of Cancer Registration in China Medical University Hospital). Patients with advanced or metastatatic cancer are ultimately refractory to chemotherapy with or without targeted therapy. Among them, more than 20 patients suffer from intractable malignant ascites which is managed by repeated paracentesis with increasing frequency. Till now, there is no reported or ongoing clinical trial to investigate the efficacy of intraperitoneal checkpoint inhibitor on the malignant ascites. Based on the previous findings and the literature review, we propose to evaluate the efficacy of immune checkpoint inhibitor (pembrolizumab) on the malignant ascites of patients with advanced gastric, pancreatic and biliary tract cancers.

The major works in the 3-year-project are summarized as:

1. Screening the candidate patients. Patients who fulfill the inclusion and exclusion criteria will be

screened. The study purpose and protocol will be explained thoroughly by physicians. Study starts only if patient read, understand and sign the inform consent.

- 2. Intraperitoneal administration of immune checkpoint inhibitor (pembrolizumab or nivolumab) per protocol followed by scheduled evaluation.
- 3. Ascites studies: Ascites cells and malignant cells in ascites are to be analyzed using flow cytometry, immunohistochemical staining, exon sequencing and total mutational burden determination.
- 4. Correlation study using clinical characteristic, ascites data and clinical response.

# **Materials and Methods:**

- 1. **Study design** : A pilot study to evaluate the effect of intraperitoneal immune checkpoint inhibitor on malignant ascites of patients with gastric, pancreatic or biliary tract cancer
- 2. Inclusion criteria
  - (1) Patients have cyto-/histologically confirmed malignant ascites from gastric, pancreatic or biliary tract adenocarcinoma
  - (2) Patients have malignant ascites more than 1000ml
  - (3) Patients have no history of prior intraperitoneal therapy for malignant ascites
  - (4) Patients have life expectancy of at least 4 weeks
  - (5) Patients have adequate platelet count  $\geq$  50,000/ul
  - (6) Women or men of reproductive potential should agree to use an effective contraceptive method
  - (7) All patients must be informed of the investigational nature of this study and must sign written informed consents.

# 3. Exclusion criteria

- (1) Patients have ascites which is related to causes other than the malignancies
- (2) Patients who are receiving intraperitoneal treatment for their malignant ascites including therapeutic paracentesis
- (3) Patients with active infection
- (4) Patients with bleeding disorders
- (5) Patient with active cardiopulmonary disease or history of ischemic heart disease
- (6) Patients have intolerant abdominal pain
- (7) Patients who have serious concomitant systemic disorders incompatible with the study, i.e. poorly controlled diabetes mellitus, auto-immune disorders, cirrhosis of the liver, and the rest will be at the discretion of in-charged investigator
- 4. Procedure

- (1) Prior to the administration of first dose immune checkpoint inhibitor (pembrolizumab or nivolumab), ascites at least 200 ml will be collected by paracentesis. The ascites will be sent for examinations listed in "ascites study". The same procedure is repeated before each administration of immune checkpoint inhibitor.
- (2) At the first 3 patients, immune checkpoint inhibitor (pembrolizumab or nivolumab) will be administered intraperitoneally at a dose of 20 mg diluted in 100 ml normal saline through a temporary catheter in 10 min (reason seen below). If there is no grade 3 or higher toxicity, the dose of pembrolizumab / nivolumab will be escalated to 50 mg for subsequent dose.
- (3) If there is no grade 3 or higher toxicity for the initial 3 patients receiving first dose 20mg of immune checkpoint inhibitor, the first dose of pembrolizumab / nivolumab will be escalated to 50 mg for subsequent patient.
- (4) The estimated initial dose for pembrolizumab / nivolumab is based on the report that both compounds were given safely to murine at a dose of 10 mg/kg. Human Equivalent Dose (HED) is 10 divided by Km ratio 12.3 = 0.8 mg/kg (Nair AB, J Basic Clin Pharm 2016). For a man with a weight 60kg, the dose will be 48 mg. Although intravenous injection of either pembrolizumab or nivolumab is well tolerated at a dose up to 10 mg/kg in previous clinical study, we reduce the initial dose of intraperitoneal infusion to 20 mg for either pembrolizumab or nivolumab.
- (5) Remove the temporary catheter after infusion.
- (6) Repeat the above procedure every 2 weeks for 1-4 times depending on the response of ascites clinically.

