# 7. Data Safety and Monitoring Plan

Data Safety and Monitoring Plan is set for ensuring the safety of patients. The plan is composed of three phases.

- (1) Screening and recruitment period
  - a. Screening patient by pre-set inclusion and exclusion criteria
  - b. Explain the current medical situation to patients, and alternative treatment methods
  - c. Obtain signed inform consent
- (2) Trial execution period
  - a. Conduction of study during hospitalization
  - b. Bedside monitoring by a physician or nurse from beginning till 10 min after administration of medication
  - c. Overnight monitoring
- (3) Follow-up period
  - a. Outpatient clinic every week till 2 weeks after the last dose of medication; then every one month for 6 m, then
  - b. Follow the patient every 2 m till end of life

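### The three-patient 20 mg toxicity gate is counted across both drugs but releases a 50 mg first dose of each; if both are used, one is released with 0 or 1 trial patient behind it

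*Protocol*

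**What the plan says.** Under Materials and Methods, 4. Procedure, item (2) gives the first three patients 20 mg of pembrolizumab or nivolumab, with a step to 50 mg at later doses if no grade 3 or higher toxicity is seen. Item (3) then governs the first dose of later patients. Its condition is "If there is no grade 3 or higher toxicity for the initial 3 patients receiving first dose 20mg of immune checkpoint inhibitor", and its consequence is that "the first dose of pembrolizumab / nivolumab will be escalated to 50 mg for subsequent patient".

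Item (4) gives the rationale. A murine dose of 10 mg/kg converts to 0.8 mg/kg in man, or 48 mg at 60 kg. As extra caution, "we reduce the initial dose of intraperitoneal infusion to 20 mg for either pembrolizumab or nivolumab".

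The Abstract, the work plan in the Background, the Procedure and item 5 (Ascites study) all refer to either drug. One sentence in the Background names only one: "we propose to evaluate the efficacy of immune checkpoint inhibitor (pembrolizumab) on the malignant ascites of patients". Nowhere does the protocol say how a patient's drug is chosen, set a minimum number per drug, keep later patients on the drug already tested, or restart a second drug at 20 mg.

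**The concern.** The gate's evidence and its release do not match. Evidence is collected on the class, whichever drug the first three patients happen to receive. The release covers each drug by name. If the first three all receive one drug and a later patient receives the other, that later patient may start at 50 mg of a drug that nobody in this trial has had by the intraperitoneal route. If the first three split two to one, the less-used drug is released on a single patient.

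At stake is the precaution in 4(4). The 20 mg start was put below a derived dose of 48 mg for either drug, and 50 mg is essentially that derived dose. For the less-used drug, the lower step can be skipped or can rest on one patient. The human tolerability that 4(4) cites is intravenous, and the intraperitoneal use cited in the Background is murine.

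**Working it through.** **Inputs from the protocol (4. Procedure).** Three patients at 20 mg; gate passed if none has grade 3 or higher toxicity; 50 mg released; murine dose 10 mg/kg; Km ratio 12.3; body weight 60 kg; intravenous dose up to 10 mg/kg.

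**The plan's own figure.** 10 / 12.3 = 0.813, rounded to 0.8 mg/kg; 0.8 × 60 = 48 mg. This reproduces.

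**Size of the released dose.**
- 50 / 20 = 2.5 times the starting dose.
- 50 / 48 = 104% of the human equivalent dose.
- 50 / (10 × 60) = 50 / 600 = 8.3% of the intravenous dose.

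**Patients behind each drug.** The possible splits (pembrolizumab:nivolumab) are 3:0, 2:1, 1:2 and 0:3. The less-used drug has 0, 1, 1 or 0 patients, so never more than one.

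**What a clean result says about one drug.** After 0 events in n patients, the exact one-sided 95% upper bound on that drug's rate is 1 − 0.05^(1/n).
- n = 3: 1 − 0.05^(1/3) = 63%.
- n = 1: 1 − 0.05 = 95%.
- n = 0: no bound.

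**Effect on the chance of passing the gate.** The protocol gives no toxicity rates, so those below are assumptions. Let p be the grade 3 or higher rate of the less-tested drug and q that of the other. The pooled gate passes with probability (1 − q)³ if the less-tested drug has 0 patients, and (1 − p)(1 − q)² if it has 1. A gate of three patients all on the less-tested drug passes with probability (1 − p)³.

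| Assumed rates | Pooled, 0 patients | Pooled, 1 patient | Own three patients |
|---|---|---|---|
| p = 30%, q = 10% | 0.9³ = 73% | 0.7 × 0.9² = 57% | 0.7³ = 34% |
| p = q = 20% | 0.8³ = 51% | 0.8³ = 51% | 0.8³ = 51% |
| p = 10%, q = 30% | 0.7³ = 34% | 0.9 × 0.7² = 44% | 0.9³ = 73% |

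Pooling is laxer in the first row, neutral in the second and stricter in the third.

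**The case against.** The best defence is that a class-wide gate is coherent. The study design defines the intervention as a class. 4(4) gives both drugs the same murine dose, the same conversion and the same starting dose. The Background supports each drug by this route in animals: "Both pembrolizumab and nivolumab have been administrated intraperitoneally without obvious toxicities in murine tumor models". 4(4) adds that "intravenous injection of either pembrolizumab or nivolumab is well tolerated at a dose up to 10 mg/kg in previous clinical study". Treatment is given in hospital, with overnight observation and "Bedside monitoring by a physician or nurse from beginning till 10 min after administration of medication". If the two drugs are about equally toxic, pooling does not change the chance of passing. The slash between the drug names may also mean only whichever drug is in use.

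Much of this stands, and it keeps the point minor. It does not close the gap. Even on the kinder reading of the slash, the count is by class and nothing limits the release to the drug tested. The protocol nowhere offers the shared class as a reason for pooling the gate.

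Three stronger readings are tempting, and the documents do not support them:
- A reader might infer that both drugs will be used. The protocol allows this but never says it, and one sentence names pembrolizumab alone.
- A reader might infer that 4(3) contradicts 4(4). It does not; it only fails to carry the 20 mg step to each drug.
- A reader might infer that pooling weakens the gate in general. It does so only if the less-tested drug is the more toxic, and nothing in the protocol suggests that either drug is.

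**Conclusion.** The point holds in conditional form. If both drugs are used, one is released at a 50 mg first dose with 0 or 1 trial patient behind it; this follows from counting and needs no assumption about toxicity. If one drug is used throughout, the problem does not arise. Confidence is high in the counting and only moderate that both drugs will be used.

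The expected harm is small, given the shared class, a released dose of about 8% of the tolerated intravenous dose, and the monitoring. The pass probabilities rest on assumed rates and show direction only. Severity is minor. It is still worth correcting, because it concerns the first dose that a patient receives and a change of wording removes it.

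**What to change.** Either of two changes is enough, and the choice is the sponsor's.

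1. Name one drug for the whole trial and make the Abstract, Background, Procedure and Ascites study agree. This costs wording only.
2. Keep both drugs. Retain 4(2) in full, including its dilution, infusion and within-patient step to 50 mg, but apply it to the first three patients on each drug. Reword 4(3) as: *For each drug separately, if none of the first 3 patients receiving a 20 mg first dose of that drug has grade 3 or higher toxicity, the first dose of that drug rises to 50 mg for subsequent patients; otherwise it stays at 20 mg.* The last clause is needed because 4(3) now states only the passing case.

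**Cost of the second option.** If both drugs are used and both gates pass, up to 2 × 3 − 3 = 3 more patients start at 20 mg. 4(6) reads "Repeat the above procedure every 2 weeks for 1-4 times depending on the response of ascites clinically". Taking this as one to four administrations in all, with 50 mg from the second dose under 4(2), their total dose compared with a 50 mg start is:
- 1 administration: 20 / 50 = 40%
- 2 administrations: 70 / 100 = 70%
- 3 administrations: 120 / 150 = 80%
- 4 administrations: 170 / 200 = 85%

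That is a small efficacy cost in a pilot whose primary endpoint is ascites reduction. If a drug's gate fails, its later patients also keep a 20 mg first dose, so the number starting low is then more than three. At an assumed 30% rate, a three-patient gate fails with probability 1 − 0.343 = 66%. The change itself requires no added enrolment, since it alters only the dose at which patients start. Three patients per drug is still a weak check; it simply applies the protocol's own 20 mg step to each drug.

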# 8. Assessment of response and toxicity

- (1) Prior to treatment, a medical history, physical examination, ascites symptoms, ascites signs, laboratory studies (blood cell count, electrolytes, liver and renal function tests, and urinalysis), chest radiography, and abdominal CT are performed.
- (2) Physical examination, ascites symptoms and ascites signs are assessed every week.
- (3) The amount of ascites is assessed by radiologists using CT which will be performed at 4th and 8th week after treatment.
- (4) Patients safety is assessed by adverse event reporting throughout the study. Adverse events

are graded according to the National Cancer Institute Common Toxicity Criteria (NCI CTCAE version 4.0).

- (5) For the analysis of the secondary endpoint, any patient lost to follow-up is censored at the time of last visit.
- 9. Correlation study of predictive factors: the association of ascites response and the characteristic of ascites, clinical features of patients and type of tumors will be analyzed.

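### Procedure item 4(3) lets new patients start at 50 mg after three clean 20 mg first doses but sets no minimum follow-up before that decision

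*Protocol*

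**What the plan says.** Section 4 (Procedure) has two separate escalation rules.

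- Item (2), within a patient: each of the opening three patients receives 20 mg, and if there is no grade 3 or higher toxicity, "the dose of pembrolizumab / nivolumab will be escalated to 50 mg for subsequent dose". Item (6) sets the spacing: "Repeat the above procedure every 2 weeks for 1-4 times depending on the response of ascites clinically".
- Item (3), between patients: "If there is no grade 3 or higher toxicity for the initial 3 patients receiving first dose 20mg of immune checkpoint inhibitor", later patients receive 50 mg as their first dose. The item states no length of follow-up, no minimum gap between patients and no rule for a patient who leaves early.

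Observation of individual patients is described elsewhere. Section 7 has "Bedside monitoring by a physician or nurse from beginning till 10 min after administration of medication", then overnight monitoring, then "Outpatient clinic every week till 2 weeks after the last dose of medication". Section 8 adds weekly examination and states: "Patients safety is assessed by adverse event reporting throughout the study". Neither section mentions the escalation decision.

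**The concern.** Item (3) is the only written condition before drug-naive patients start at 2.5 times the initial dose (50/20). Absence of toxicity means something only over a stated period, and none is stated. If the fourth patient is ready the day after the third is dosed, the decision rests on one night's observation of that third patient.

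The two rules also sit oddly together. A patient who has already tolerated 20 mg waits two weeks before 50 mg, while a patient with no exposure on study may get 50 mg with no wait. The less-tested patient has the weaker safeguard, which looks like an omission rather than a choice.

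The matter belongs in the protocol, because a dose-escalation rule is not something a statistical analysis plan would normally supply. The Background says that "there is no reported or ongoing clinical trial to investigate the efficacy of intraperitoneal checkpoint inhibitor on the malignant ascites", and the intraperitoneal data it cites are from mice, so the first few patients carry much of the information on this route.

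**Working it through.** The protocol gives no operating characteristics for the rule, so there is no figure of its own to reproduce. The textual finding needs no arithmetic. The calculation below only sizes it, and its rates are assumptions.

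**Inputs**
- From the protocol: three patients, none with grade 3 or higher toxicity (item (3)); 14-day dosing interval (item (6)); weekly clinic (Section 7).
- Assumed: true grade 3 or higher rate t = 5%, 10% or 30% over 14 days. The share of that toxicity visible s days after the dose is G(s) = g0 + (1 - g0) × min(s/14, 1), with g0 = 0 or 0.5 visible overnight.
- Assumed: accrual of 5, 10 or 20 starts a year at random (Poisson) times. The Background reports that "more than 20 patients suffer from intractable malignant ascites which is managed by repeated paracentesis with increasing frequency", but this does not give an enrolment rate.

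**1. How often is the fourth patient ready early?** P(within d days of the third) = 1 - exp(-rate × d/365).

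| Starts a year | Mean gap (days) | Within 7 days | Within 14 days |
|---|---|---|---|
| 5 | 73 | 9% | 17% |
| 10 | 36.5 | 17% | 32% |
| 20 | 18.25 | 32% | 54% |

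**2. Full follow-up.** P(release) = (1 - t)^3: 0.95^3 = 85.7%; 0.90^3 = 72.9%; 0.70^3 = 34.3%.

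**3. Fourth patient starts the day after the third, the first two fully observed.** P(release) = (1 - t)^2 × (1 - t × g0), shown for g0 = 0.5 to g0 = 0.
- t = 5%: 88.0-90.3%, against 85.7%
- t = 10%: 77.0-81.0%, against 72.9%
- t = 30%: 41.7-49.0%, against 34.3%

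**4. Averaged over random arrival times.** Mean of the product of (1 - t × G(s_i)) over the three patients, with exponential gaps, by simulation. The table gives the rise over step 2 in percentage points, for g0 = 0.5 to g0 = 0.

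| Starts a year | t = 5% | t = 10% | t = 30% |
|---|---|---|---|
| 5 | 0.2-0.4 | 0.4-0.8 | 0.7-1.4 |
| 10 | 0.4-0.9 | 0.8-1.6 | 1.4-2.9 |
| 20 | 0.9-1.7 | 1.6-3.2 | 2.9-6.1 |

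**5. Early leavers who still count, taken separately.** With loss q and a share f of leavers' toxicity seen, P(release) = (1 - t(1 - q(1 - f)))^3. For q = 5-10% and f = 0.5 to 0, this gives 86.1-87.1%, 73.5-75.4% and 35.4-38.9% at t = 5%, 10% and 30%: a rise of about 0.3-5 points.

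**The case against.** The strongest reply is that little turns on this.

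- **Accrual is probably slow.** The patients counted in the Background are managed by repeated paracentesis. Exclusion criterion (2) bars patients receiving therapeutic paracentesis, and inclusion criterion (3) bars prior intraperitoneal therapy. Rates of 10-20 starts a year are therefore likely too high. This stands, and is why 5 a year is shown.
- **Three patients cannot measure toxicity anyway.** With 0 of 3 events, the one-sided 95% upper limit is 1 - 0.05^(1/3) = 63%, with or without a follow-up period. True, but that is no reason to decide before the three have been followed.
- **Some 50 mg experience will already exist.** At 10-20 starts a year, patient 1 is at least 14 days past the first dose in 96-99% of cases when patient 4 arrives. If redosed, patient 1 will usually have had 50 mg. This reassures in practice, but item (3) does not depend on it.
- **The dose is modest.** The protocol cites intravenous tolerance up to 10 mg/kg, which is 600 mg at 60 kg, or 12 times 50 mg. That makes high toxicity less likely, but concerns another route.

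A reader might also infer more than the text supports:
- That patients go unobserved. They do not, and toxicity seen overnight or in clinic would block the step.
- That the protocol authorises a start within days. It only fails to prevent one.
- That the route has never been tried in patients. The Background speaks only of trials of efficacy on malignant ascites.
- That item (2) is unsafe. It is already conditional on no grade 3 or higher toxicity, and weekly examination continues.
- That the missing replacement rule is a major flaw. Step 5 shows it is marginal, and much higher loss within 14 days is unlikely given entry at 4 weeks' life expectancy.

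**Conclusion.** The point holds as a gap in the escalation rule: item (3) sets no minimum follow-up, and no other section ties the existing monitoring to the decision. This rests on the text alone.

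Its average size is small: about 0.2-3 percentage points on the chance of release at toxicity rates of 5-10% and 5-20 starts a year. It is larger only when the fourth patient starts within days (up to about 15 points at 30% toxicity, 49.0% against 34.3%) or when toxicity is high and accrual fast (about 6 points). These sizes depend on assumed toxicity, onset and accrual, none of which the protocol gives. It is a worthwhile, inexpensive safety amendment and does not undermine the study.

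**What to change.** **Item (3).** Start no patient at 50 mg until three patients have each completed 14 days after a first 20 mg dose without grade 3 or higher toxicity. Any such toxicity seen before the decision counts against escalation. A patient who leaves, or dies of disease, within 14 days without such toxicity does not count among the three and is replaced at 20 mg. A patient ready to start while the 14 days run starts at 20 mg and can serve as the replacement.

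**Item (2).** Extend it from the opening three patients to every patient started at 20 mg; otherwise the second dose of anyone started during the waiting period is undefined.

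Fourteen days is a choice; it is proposed because it matches the existing dosing interval and weekly visits.

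**Cost.**
- No new visits, and a delay of up to 14 days before the first 50 mg start (longer if a replacement is needed).
- Expected patients starting at 20 mg meanwhile = rate × 14/365: 0.19, 0.38 or 0.77 at 5, 10 or 20 starts a year.
- Replacements add on average at most 3/(1 - q) - 3 = 0.16 starts at 5% loss, or 0.33 at 10%.
- The rule becomes slightly conservative. At 30% toxicity, release falls from 34.3% to 32.6% with 10% loss and half of leavers' toxicity seen. With no loss, it falls to about 29-32% if toxicity in patients started during the wait also counts (10-20 starts a year).
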